12.5 DEFINITION OF SOURCE DATA

The data source for the analyses of the primary and secondary endpoints will be medical records and the study specific source documents for the study. Source data will be where the information is first recorded at the investigative site.

13 STATISTICAL CONSIDERATIONS

13.1 STATISTICAL AND ANALYTICAL PLANS

The material of Section 13 of the clinical trial protocol is the basis for the statistical analysis plan for the study. This plan may be revised during the study to accommodate clinical trial protocol amendments and to make changes to adapt to unexpected issues in study execution and data that affects planned analysis. These revisions will be based on a review of the study data, and a final plan will be issued before database lock. Complete details of the statistical analyses and methods, including data conventions, will be contained in a separate and final statistical analysis plan.

13.2 DETERMINATION OF SAMPLE SIZE

FINAL Protocol Amendment 1 - Version 24 April 2015 This document contains confidential, proprietary information.

13.3 ANALYSIS VARIABLES

13.3.1 Demographic and baseline characteristics

Demographic and baseline characteristics include subjects' sex, race/ethnicity, age, height, weight, medical history, prior and concomitant medications, length of NLFs and other facial wrinkles, and vital signs (sitting heart rate and blood pressure).

13.3.2 Safety variables

13.3.2.1 Adverse events

The co-primary safety endpoints are:

- 1. The percentage (incidence rate) of subjects with any injection site nodule and/or papule over 5 years.
- 2. The percentage (incidence rate) of subjects with any of the following injection site events over 5 years:
 - Hypertrophic scarring
 - Keloid formation
 - Changes in the skin pigmentation at the site of injection compared to adjacent skin
 - Granuloma (confirmed by a biopsy)
 - Skin necrosis
 - Hypersensitivity reactions
 - Unexpected change in wrinkle contour

The injection site adverse events listed above are defined as adverse events of interest in this study.

The secondary safety endpoints are the percentages (incidence rate) of subjects with any injection site nodule and/or papule, the percentage of subjects who experienced any adverse events of interest other than nodule or papule over 2 years; location and intervention for any adverse events of interest; adverse event severity, duration, time to onset of adverse event, relationship to Sculptra® Aesthetic and relationship to injection procedure during the course of the study.

13.3.2.2 Laboratory safety variables

A urine pregnancy test for women of child-bearing potential will be collected at Visit 1.

13.3.2.3 Vital signs and physical exam

Vitals signs (sitting heart rate and blood pressure) and physical examination (overall subject assessment and facial assessment) will only be collected at Visit 1 and considered as the baseline characteristics for each subject (see Section 13.3.1).

13.3.2.4 Other safety variables

None.

13.3.3 Efficacy variables

13.3.3.1 Primary efficacy variables

None.

13.3.3.2 Secondary efficacy variables

The secondary efficacy endpoints are:

- Change from baseline to post-treatment follow-up time points in the WAS at Month 6, Month 13, and Years 2, 3, 4, and 5.
- Investigator/Subject Global Assessments Scores at Month 6, Month 13, and Years 2, 3, 4, and 5.

13.4 ANALYSIS POPULATIONS

The intent-to-treat (ITT) population, per protocol (PP) population, and Completer2 and Completer5 populations are defined as follows:

13.4.1 Efficacy populations

The analysis populations for efficacy will be the ITT population that consists of all subjects who receive at least one Sculptra® Aesthetic injection; the PP population will consist of all subjects who receive at least 1 Sculptra® Aesthetic injection and are without any major protocol deviation.

13.4.2 Safety populations

The analysis population for safety will also include the ITT population and the PP population. The ITT population is the primary population for hypothesis testing.

13.4.3 Other analysis populations

The Completer2 population consists of all subjects who receive at least 1 Sculptra® Aesthetic injection and finish the second year visit.

The Completer5 population consists of all subjects who receive at least 1 Sculptra® Aesthetic injection and finish the fifth year visit.

13.4.4 Disposition of subjects

The general disposition of subjects during the study will be defined as follows: (a) **screened** subjects are those who have a written informed consent document; (b) **treated** subjects are those screened subjects who received at least 1 dose of Sculptra® Aesthetic; and (c) **completed** subjects are those treated subjects who complete all clinical trial protocol required visits.

13.5 STATISTICAL METHODS

13.5.1 Demographics and baseline characteristics

Demographics and baseline characteristics will be summarized by descriptive statistics, which consist of mean, standard deviation, median, minimum and maximum for continuous variables or frequency count and percentage for categorical variables.

13.5.2 Extent of study treatment exposure and compliance

[figure not shown]
Extent of treatment exposure and compliance will be determined by the number of injection sessions, duration of treatment period (days), the total amount of Sculptra® Aesthetic used, the total amount of Sculptra® Aesthetic used per injection site and the amount of Sculptra® Aesthetic used per surface area per WAS. They will all be summarized by descriptive statistics.

13.5.4 Analysis of safety data

FINAL Protocol Amendment 1 - Version 24 April 2015 This document contains confidential, proprietary information.

FINAL Protocol Amendment 1 - Version 24 April 2015 This document contains confidential, proprietary information.

13.5.4.2 Other analyses of adverse events

All adverse events will be collected and summarized with the number of subjects reporting adverse events by number of injections, system organ class, preferred term, severity, and relationship to the Sculptra® Aesthetic or injection procedure as well. Time to onset of the first adverse event of interest and the duration of adverse event of interest (maximum duration if there are multiple adverse events of interest with a subject) will be summarized by Kaplan-Meier plots.

Treatment-emergent adverse events (TEAEs) are defined as adverse events that develop or worsen during the on-treatment period (time from first dose of Sculptra® Aesthetic to the end of the study). All adverse events will be coded using the current version of MedDRA.

The following frequency distributions of adverse events (incidence tables) will be provided:

- Overview of adverse events
- All TEAEs by number of injections
- All TEAEs by system organ class and preferred term
- All TEAEs by system organ class and preferred term by decreasing frequency
- All TEAEs by preferred term by decreasing frequency
- All TEAEs by system organ class, preferred term and intensity
- Possibly related TEAEs by system organ class, preferred term and intensity

The following listings will be provided for the ITT population:

- All adverse events
- Serious adverse events

Protocol GLI.04.SPR.US10321

CONFIDENTIAL

- adverse events that resulted in death
- adverse events that lead to discontinuation of Sculptra® Aesthetic
- Nodules and papules
- adverse events of interest, other than nodule and papule

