Subjects treated with Sculptra® Aesthetic and Cosmoplast during the controlled phase showed a consistent, progressive, and significant improvement over baseline for the primary variable WAS beginning 3 weeks after the last treatment. Though the treatment effect of Sculptra® Aesthetic was maintained for up to 13 months, the Cosmoplast treatment effect returned to baseline within 3 months of the final treatment.

Commonly occurring short-term injection-related site reactions were reported in both treatment groups. In this clinical study the percentage of subjects with nodules and/or papules was greater after Sculptra® Aesthetic (17.2% [20 of 116]) than after the control treatment (12.8% [15 of 117]). This reflects 8 Sculptra® Aesthetic subjects who experienced nodules, 10 Sculptra® Aesthetic subjects who experienced papules, and 2 Sculptra® Aesthetic subjects who experienced both nodules and papules. After the first Sculptra® Aesthetic injection session, time to onset for nodules was 160 days (median) and 209 days (mean), and for papules, time to onset was 55 days (median) and 159 days (mean). After Sculptra® Aesthetic injection, the duration of nodules was 100 days (median) and 180 (mean) days, and for papules, was 110 days (median) and 176 days (mean). One subject with a papule required a single intralesional corticosteroid injection and the event resolved. For 3 subjects with nodules/papules, no information on outcome was available at the end of the 25-month extension phase study. For all remaining subjects, nodules/papules resolved spontaneously. None of these events were reported as a serious adverse event by the investigator. Table 3 shows adverse event data that were collected from patient diaries over the controlled phase (0 to 13 months Sculptra® Aesthetic versus Cosmoplast).

CONFIDENTIAL

Table 3 - Intensity of adverse events after the initial treatment session, recorded in the 14 day subject diary (Controlled Phase) - All-Treated Population

SCULPTRA Aesthetic (First Treatment Session: N = 116)						Cosmoplast (First Treatment Session: N = 117)						
		Severity of A	dverse Eve	nt ^a			Severity of Adverse Event ^a					
Injection Procedure Related Event	Total subjects reporting symptoms ^a n (%)	Mild n	Moderate n	Severe n	Missing n	Total subjects reporting symptoms ^a n (%)	Mild n	Moderate n	Severe n	Missing n		
Localized Swelling	94 (81.0)	64	24	5	1	76 (65.0)	60	13	1	2		
Localized Tenderness	94 (81.0)	63	24	2	5	83 (70.9)	62	16	1	4		

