5 STUDY OBJECTIVES

5.1 PRIMARY

The primary objective of the study is to assess the long-term safety of Sculptra® Aesthetic in immune-competent subjects as a single regimen for correction of WAS 2 to 4 NLF contour deficiencies and other facial wrinkles in which deep dermal grid pattern (cross-hatch) injection technique is appropriate, for the following variables:

- The device-related long-term incidence of chronic inflammation (nodules, papules, granulomas, skin necrosis, hypersensitivity, and other injection site reactions) in subjects with Fitzpatrick skin type I-VI.
- The incidence of hypertrophic scarring, keloid formation, and changes in skin pigmentation in subjects with Fitzpatrick skin type IV-VI.

5.2 **SECONDARY**

Secondary objectives include the following:

- To evaluate the time to onset, duration, severity, relationship to Sculptra® Aesthetic and/or injection procedure, and outcome of all adverse events, including adverse events mentioned under the primary objectives, during the course of the study, by Fitzpatrick skin type.
- To evaluate the change in the WAS from baseline to post-treatment follow-up time points at Months 6, 13, and Years 2, 3, 4, and 5 in NLFs and other facial wrinkles.
- To evaluate Investigator/subject global assessments at Months 6, 13, and Years 2, 3, 4, and 5.

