4.4.4 Analysis of safety data

4.4.4.2 Other analyses of adverse events

All adverse events will be collected and summarized with the number of subjects reporting adverse events by number of injections, system organ class, preferred term, severity, relationship to the Sculptra® Aesthetic, and relationship to injection procedure.

For injection site nodules and/or papules and any other AEI, summaries will also include incidence rates by location and intervention, duration (<=30 days versus >30 days), and time to onset (<=30 versus >30 days for nodules and/or papules, and <=120 versus >120 days for any other AEI). Duration and time to onset of all events will also be summarized with descriptive statistics. Kaplan Meier estimates and plots will also be provided to estimate the maximum duration and time to the first occurrence within a subject. Time to onset is defined as the time from first injection to the start of the event.

To obtain duration of injection site nodules and/or papules and any other AEI, events that are ongoing will be handled in two ways: 1) excluding events that are ongoing at the time of data cutoff; and 2) assigning data cutoff date as the event end date.

The following frequency distributions of adverse events (incidence tables) will be provided:

- Overview of adverse events
- All AEs by number of injection sessions
- All AEs by system organ class and preferred term by decreasing frequency
- All AEs by system organ class, preferred term and intensity
- All AEs by system organ class, preferred term and relationship to treatment
- All AEs by system organ class, preferred term and relationship to procedure

The following listings will be provided:

- All adverse events
- Serious adverse events
- Adverse events that lead to discontinuation of Sculptra® Aesthetic
- Adverse events that lead to discontinuation of study
- Injection site nodules and papules
- AEI, other than injection site nodule and papule

The incidence rate of injection site nodule and/or papule will also be summarized by study site and baseline wrinkle assessment.

Subject reported injection related events collected in the diary card will be summarized by frequencies and percentages. Severity of subject reported injection related events after initial treatment session will be summarized by anatomic areas and Fitzpatrick skin type groups.

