5.3 Relative Day Ranges and Visit Windows

If a subject discontinues early, the efficacy data (wrinkle assessments and investigator/subject global evaluations) from Visit 12 (Year 5) will be reassigned to a scheduled visit based on the relative ranges in the following table. If a result already exists for the calculated visit or the calculated visit was not a scheduled visit, the next scheduled visit will be assigned.

Relative day calculations will be the parameter visit date of interest minus the Study First Treatment Date plus one.

Table 1: Visit Collection Time and Relative Day Ranges

Collection Time (Target Day ± Visit Window)	Relative Day Ranges
Baseline (Day 1)	≤ Day 1
Week 3 (Day 22 ± 3 days)	Day 2 to Day 32
Week 6 (Day 43 ± 3 days)	Day 33 to Day 53
Week 9 (Day 64 ± 3 days)	Day 54 to Day 124
Month 6 (Day 184 ± 2 weeks)	Day 125 to Day 290
Month 13 (Day 397 ± 2 weeks)	Day 291 to Day 564
Year 2 (Day 731 ± 4 weeks)	Day 565 to Day 913
Year 3 (Day 1096 ± 4 weeks)	Day 914 to Day 1278
Year 4 (Day 1461 ± 4 weeks)	Day 1279 to Day 1643
Year 5 (Day 1826 ± 4 weeks)	≥ Day 1644

5.4 Calculation of Duration and Time to Onset:

Below are the rules on how duration and time to onset are calculated:

- 1. Duration = Event End Date Event Start Date + 1
 - For events that are ongoing, the formula will be updated per following scenarios:
 - a. If the subject had XXX visit, duration will be XXX visit date minus start date plus 1;
 - b. If the subject discontinued the study, duration will be discontinuation date minus event start date plus 1;

- c. If none of the above, the event's duration will be time of visit minus study day of event start date plus 1, where time of visit is defined as scheduled study day + 4 weeks (2 weeks for Month 13).
- 2. Time to Onset (from treatment) = Event Start Date Date of First Treatment.

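### The only Kaplan-Meier duration analysis is of each subject's longest event of interest, so the objective of adverse event duration has no visible estimate that allows for ongoing events

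*Protocol*

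**What the plan says.** The secondary objective in Protocol 5.2, repeated in SAP 3.2, is "To evaluate the time to onset, duration, severity, relationship to Sculptra® Aesthetic and/or injection procedure, and outcome of all adverse events", by Fitzpatrick skin type. Protocol 13.3.2.1 lists adverse event duration among the secondary safety endpoints.

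Three pieces of analysis text bear on duration:

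- **Kaplan-Meier.** Protocol 13.5.4.2 says "duration of adverse event of interest (maximum duration if there are multiple adverse events of interest with a subject) will be summarized by Kaplan-Meier". SAP 4.4.4.2 agrees: "Kaplan Meier estimates and plots will also be provided to estimate the maximum duration and time to the first occurrence within a subject".
- **Event-level summary.** SAP 4.4.4.2 adds: "Duration and time to onset of all events will also be summarized with descriptive statistics". It also splits incidence by duration at 30 days. SAP 6.0 confines duration analysis to the adverse events of interest and declares this as a change from the protocol.
- **Ongoing events.** SAP 4.4.4.2 gives a pair of rules for them: "1) excluding events that are ongoing at the time of data cutoff; and 2) assigning data cutoff date as the event end date". SAP 5.4 adds: "If the subject discontinued the study, duration will be discontinuation date minus event start date plus 1". Otherwise the duration runs to the visit date or to a scheduled day plus the visit window.

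No visible text says that an ongoing event is censored, and none plans a Kaplan-Meier with one record per event. Protocol 13.5.4.1 and SAP 4.4.4.1 are blacked out. SAP 6.0 describes Protocol 13.5.4.1 as holding the primary hypotheses and the covariate comparison for multiple imputation, so a duration analysis there is unlikely.

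**The concern.** The objective asks how long adverse events last. The maximum within a subject answers a different question: how long the worst event lasts in an affected subject. The two coincide only for subjects with one event. With several, the maximum rises with the count even when no single event lasts longer. If one Fitzpatrick group has more recorded events per subject than another, its longest-event durations will be greater even when event durations are the same.

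The event-level summary could fill this gap, but its stated rules do not allow for follow-up that is still running. Leaving out ongoing events removes the long ones preferentially. Ending them at cutoff or discontinuation records a shorter duration than the true one. Both push duration down, most of all at the early interim looks.

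A smaller technical point concerns the maximum itself. If a subject's longest record has ended while a shorter one is still running, the subject may be scored as ended although the running event could outlast it. The plan does not say how such a subject is scored.

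**Working it through.** The plan gives no duration figure to reproduce. What follows is an illustration, not a forecast.

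**Inputs.** Protocol section 4 gives the pivotal nodule duration (median 100 days, mean 180) and onset (median 160, mean 209). Of 20 affected subjects in that study, 8 had nodules, 10 had papules and 2 had both. That is 2/20 = 10% with both event types, the only figure on multiplicity in the documents. It does not count several events of one type.

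**Assumed model.** Event durations are lognormal. Mean/median = exp(σ²/2), so σ = √(2 ln(180/100)) = √1.1756 = 1.084.

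**1. Median of the longest event.** Let a share p of affected subjects have two independent events and the rest one. With F the distribution function of a single duration, the median of the maximum solves (1 − p)F + pF² = 0.5. This gives F = [p − 1 + √(1 + p²)]/(2p), and the median is 100 × exp(1.084 × Φ⁻¹(F)).

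| Share with two events | F | Median of longest event (days) |
|---|---|---|
| 0 | 0.500 | 100 |
| 10% | 0.525 | 107 |
| 50% | 0.618 | 138 |
| 100% | 0.707 | 181 |

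The median duration of a single event is 100 days in every row. In the last row, simulated within-subject correlation of 0.5 or 0.8 on the log scale lowers 181 to 153 or 131.

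**2. Event-level summaries.** Simulation used lognormal onset (median 160, mean 209) and no dropout; the true median / mean is 100 / 180 days.

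| Look | Events ongoing | Ongoing excluded: median / mean | Ended at cutoff: median / mean | Event-level Kaplan-Meier median, ongoing censored |
|---|---|---|---|---|
| Month 13 | 27% | 72 / 90 | 88 / 113 | 100 |
| Year 2 | 8% | 90 / 129 | 99 / 152 | 100 |
| Year 5 | 0.6% | 99 / 169 | 100 / 176 | 100 |

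The near agreement at Year 5 rests on there being no dropout. Planned enrolment is 863 for 604 evaluable subjects, and 1 − 604/863 = 30%. A subject who leaves with an event running is cut at discontinuation, so dropout would widen the gap. I have not put a size on that.

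**3. Bias in the maximum from a shorter event still running.** Simulated under the same model and onset; the figure is the share of subjects whose longest event exceeds 180 days.

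| Share with two events | Month 13: true / longest-record curve | Year 5: true / longest-record curve |
|---|---|---|
| 10% | 0.311 / 0.309 | 0.313 / 0.313 |
| 50% | 0.383 / 0.374 | 0.396 / 0.396 |

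This bias is small and disappears by Year 5.

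**The case against.** The maximum is declared openly in both documents and does not claim to be event duration. It is coherent with co-primary endpoints that count subjects. It is also robust to record-keeping: if a site enters one cluster as five records of equal length, the maximum is unchanged, whereas an event-level curve gives that subject five times the weight. Protocol 10.5 asks for symptoms to be grouped where possible, and no visible rule makes each lesion a record. If subjects with more events also have longer ones, an event-level curve is tilted toward them, and a clustered variance does not correct that. All of this stands. It is a reason to keep the maximum and to add to it, not to replace it.

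The SAP does plan event-level descriptive statistics, so duration is not ignored. That also stands, but those statistics do not allow for ongoing events.

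A reader might infer more than the documents support:

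- **That medians of 181 days or more should be expected.** This needs every affected subject to have at least two independent events. The one available figure is 10% with both event types.
- **That sites with more events will look worse on duration.** The by-site summary in SAP 4.4.4.2 is of nodule and papule incidence. No by-site duration curve is planned in the visible text.
- **That the maximum is materially biased low.** Step 3 shows otherwise at modest multiplicity, and the scoring behind that bias is a silence in the plan, not a stated rule.
- **That comparison with the pivotal durations is ruled out.** The protocol does not say whether those figures are per event or per subject, or how ongoing events were treated. The SAP's descriptive statistics remain available for such a comparison.

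**Conclusion.** The point holds as a gap in the plan. The visible text gives no estimate of adverse event duration that is both event-level and censoring-aware. The Kaplan-Meier analysis has a different target, and the event-level summary truncates or drops ongoing events.

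The consequence is modest. With independent lognormal durations at the pivotal nodule values, the longest-event median exceeds the event median by about 7% if 10% of affected subjects have two events, 38% if half do and 81% if all do, and by less with within-subject correlation. The descriptive summaries fall furthest short at Month 13, with medians of 72 or 88 days against 100. The multiplicity, the lognormal shape and the independence are assumptions; only the pivotal medians and means come from the documents. The co-primary endpoints are unaffected. This is a worthwhile improvement to a secondary analysis, not a fault that threatens the study's conclusions.

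**What to change.** In SAP 4.4.4.2, add a Kaplan-Meier analysis of time to resolution with one record per event, as follows:

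- Analyse the two planned groups separately (injection site nodules and/or papules; other events of interest), overall and by Fitzpatrick group (I-III, IV, V-VI).
- Right-censor ongoing events at last contact, and state this rule explicitly.
- Take confidence intervals from a subject-clustered variance (robust or bootstrap).
- Report the distribution of recorded events per subject beside the curve, because event-level weights depend on how sites group or split records.

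Keep the per-subject maximum as planned, labelled as the longest event per subject, and state how a subject is scored when a shorter event is still running.

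The cost is SAP wording and a little programming. Onset and resolution dates are already collected under Protocol 9.1.1. The added curve has its own weakness, its dependence on recording practice, which is why it should supplement the maximum and not displace it.
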